ADHERENCE TO SECONDARY PREVENTION MEDICATIONS AND FACTORS INFLUENCING ADHERENCE, AFTER ACUTE CORONARY SYNDROME (ACS) IN PATIENTS ATTENDING A TERTIARY CARE CENTRE OF NEPAL: A DESCRIPTIVE CROSS SECTIONAL STUDY

2. Project summary (~250 words)

This study aims to assess adherence to secondary prevention medications among patients in Nepal following an Acute Coronary Syndrome (ACS) event and identify factors affecting adherence. ACS, a major cause of morbidity and mortality globally and in Nepal, requires effective secondary prevention to minimize recurrent cardiovascular events. However, adherence to prescribed medications remains low, especially in low- and middle-income countries like Nepal. Poor adherence can lead to increased healthcare burden, worsened patient outcomes, and higher mortality rates. To address this, the study will evaluate patients' medication adherence through the MYMEDS questionnaire, a self-reported tool, which has been positively received for its simplicity and clarity.

Conducted at the Manmohan Cardiothoracic Vascular and Transplant Centre in Nepal, the study will involve a sample of adult patients readmitted or attending follow-ups post-ACS. Convenience sampling will be used, targeting approximately 117 patients to account for non-responses. The research will gather data on patient demographics, socioeconomic factors, clinical characteristics, and self-reported adherence barriers, analyzing these with SPSS to assess correlations with clinical outcomes.

The expected 12-month project will consist of phases for ethical approvals, data collection, analysis, and report dissemination. By identifying key barriers to adherence, the study aims to inform targeted interventions that could enhance medication adherence, improve long-term cardiovascular outcomes, and reduce healthcare burdens in Nepal and other similar settings.

3. Introduction

Patients experiencing myocardial infarctions (MI) are at risk of subsequent cardiovascular events and prevention of recurrent events is a major clinical and public health priority (1).

Pharmacological therapy plays a key role in the secondary prevention of CVD and improve long term outcomes particularly in patients who have not undergone revascularization via percutaneous coronary intervention (PCI) (2–4). Large evidence supports drugs conferring mortality benefit from several different classes: antiplatelet agents, angiotensin-converting enzyme inhibitors (ACEIs)/angiotensin receptor blockers (ARBs), beta blockers and lipid-lowering drugs (5–7).

Adherence to secondary prevention medications following acute coronary syndromes (ACS) is a predictor of future major adverse cardiovascular events. Medication usage (and its success) requires the coordination of the behaviours of both treating physicians and patients, particularly with regards to adherence. Underutilisation of these medications is associated with higher risk of major adverse cardiovascular events globally (8). Patients' poor adherence to their medication is a complex problem for health care services, especially in the care of heart diseases, for which the correct and effective treatment is essential for a patient's quality of life and survival rate(9). A study had shown that patients who recently experienced a myocardial infarction (MI) and did not adhere closely to their prescribed regimen were 2.6 times more likely to die within a year following the MI compared with those who followed their regimen more closely (10).

Medication adherence has been studied extensively over the past decades. Numerous reports in the literature had estimated that by 12 months, adherence to cardioprotective therapy had dropped to less than 50% across several classes of drugs including statins and ACE-Inhibitors(11). Some of the predictors of non-adherence most often cited include polypharmacy, frequency of medication changes, socioeconomic status, cost, household composition, comorbidity, and accessibility to medical care (12). Gaining an understanding of the key factors that influence adherence among patients post-ACS may allow treating physicians to tailor their treatment approach and implement effective hospital interventions to improve patient adherence and, subsequently, CV outcomes(13).

Various kinds of tools have been used to assess patients's adherence to medication, of these, one of the most convenient and easiest way is self-reporting. The 'My Experience of Taking Medicines' (MYMEDS) questionnaire is a recently developed self reporting tool for identifying modifiable adherence barriers among individuals prescribed post-myocardial infarctions secondary prevention medicines (SPM). The MYMEDS questionnaire received positive feedback from 131 patients, with 96.9% stating it helped them consider their medications, 97.7% finding it simple and clear, and 99.2% agreeing the length was acceptable. Patients felt it improved understanding of their therapies and facilitated meaningful consultations (14).

4. Rationale and Justification of study

Acute Coronary Syndrome (ACS) is a leading cause of morbidity and mortality globally, and Nepal is no exception (15). Despite advancements in medical treatments, secondary prevention remains a critical aspect of managing patients post-ACS to reduce the risk of recurrent cardiovascular events. However, adherence to these medications remains suboptimal, especially in low- and middle-income countries like Nepal, leading to a higher incidence of recurrent cardiovascular events and increased healthcare burden(16).Several factors contribute to poor adherence to secondary prevention medications in Nepal. In Nepal, where healthcare infrastructure is still developing, adherence to long-term medications is

particularly challenging for patients, especially in rural and underserved regions (16). This research is critically needed to address the growing burden of cardiovascular disease in Nepal by exploring the current state of adherence to secondary prevention medications after ACS. Understanding the extent and factors contributing to poor adherence will help in identifying key barriers and implementing targeted interventions. Given the paucity of data on this topic in Nepal, this research will not only fill a crucial gap in the literature but also help guide clinicians and healthcare administrators in developing effective strategies for enhancing secondary prevention efforts. The findings could have broader implications for improving long-term cardiovascular outcomes in low- and middle-income countries with similar healthcare challenges.

In summary, this study is essential for understanding why patients in Nepal fail to adhere to life-saving medications post-ACS and what can be done to mitigate this problem, ultimately improving patient care and reducing the burden on the healthcare system.

5. Objectives

a. General objectives:

To assess the level of adherence to prescribed secondary prevention medications and identify the factors influencing adherence among patients with Acute Coronary Syndrome (ACS) in Nepal.

b. Specific objectives:

- **To assess the level of adherence to secondary prevention medications (SPMs) among patients discharged after an Acute Coronary Syndrome (ACS) event, including antiplatelets, statins, beta-blockers, and ACE inhibitors/ARBs.**
- **To explore the influence of patient demographic factors** (such as age, gender, education level, occupation, and place of residence) and clinical characteristics (type of ACS, comorbidities) on medication adherence.
- **To identify patient-reported barriers to medication adherence**, including concerns about medication side effects, pill burden, practical issues with medication administration, and difficulties in integrating medications into daily routines.
- **To evaluate the relationship between medication adherence and clinical outcomes**, such as recurrent cardiac events, rehospitalization.

6. Research questions/hypothesis

- What is the level of adherence to secondary prevention medications among Acute Coronary Syndrome (ACS) patients in Nepal, and what demographic, clinical, and patient-reported factors influence this adherence and its associated clinical outcomes?

7. Research design and Methodology

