7.3 Study population/Sampling frame

A sample of adult patients (age ≥ 18 years) who have either come to OPD for follow-up or have been readmitted for having cardiac complications months after surviving ACS (including STEMI, NSTEMI, and unstable angina) in Manmohan Cardiothoracic Vascular and Transplant Centre, Nepal will be selected via **convenience sampling**. The total population under study is around 1000.

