7.4 Study site and its justification

This descriptive cross-sectional study will be conducted at Manmohan Cardiothoracic Vascular and Transplant Centre, a premier tertiary care institution in Nepal, specializing in cardiovascular care. As one of the nation's leading centres for heart disease management, it offers advanced diagnostic, therapeutic, and surgical services to patients with a wide spectrum of cardiovascular conditions, including Acute Coronary Syndrome (ACS). The centre's reputation for excellence in cardiology and its strategic location make it an ideal setting for research into adherence to secondary prevention medications after ACS.

The patient population at this centre is diverse, including individuals from both urban and rural areas of Nepal, which provides a comprehensive understanding of medication adherence patterns across various demographic and socioeconomic groups. The centre regularly follows up with ACS survivors, both through outpatient visits and during readmissions for cardiac complications. This makes it a prime location to study patients who have either come for follow-up visits or been readmitted within 12 months of their initial ACS event, including STEMI, NSTEMI, and unstable angina.

By focusing on this centre, the research will leverage the expertise of its specialized staff and access to detailed patient records, providing valuable insights into medication adherence in real-world clinical practice. These insights can then be used to inform targeted interventions to improve long-term outcomes for ACS survivors across Nepal.

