7.5 Sampling method

In our research study, we will employ convenience sampling. Convenience sampling is a non-probability method where units are selected for inclusion in the sample because they are the easiest for the researcher to access. The target population consists of adult patients (age ≥ 18 years) who have either come to OPD for follow-up or have been readmitted in hospital for having cardiac complications months after surviving ACS (including STEMI, NSTEMI, and unstable angina). Rather than applying specific

stratification based on cancer type, we will approach patients who are readily available within the hospital setting. We will use the MYMEDS questionnaire. The researcher will personally ask all the questions and fill out the questionnaire for each eligible patient. To assess the socioeconomic status of participants, we will utilize the Modified Kuppuswamy's Socioeconomic Status Scale, adapted to the context of Nepal (18). Alongside demographic information such as gender, age at diagnosis, and marital status, we will collect data on education level, occupation, and family income, as per the scale's criteria(18).

Once we collect the responses, we will use MS Excel for data entry and analyze the data using SPSS version 29.

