	c. I have difficulties or problems getting my repeat prescriptions and would like help ordering them from my GP or pharmacy.				
	d. I have difficulties or problems reading the label on the medicines bottle or box and would like a solution or alternative.				

Section 5: Fitting medicines into daily routine	a. I sometimes forget to take my heart medicines.				
	b. I am finding it difficult to fit one or more of my heart medicines into my daily routine.				
	c. I feel inconvenienced/bothered about sticking to all my heart medicines.				

Section 6: Adherence to Individual SPMs

For each of your prescribed medicines (SPMs), please indicate how often you have taken them as prescribed in the PAST MONTH:

Medication	All of the Time	Nearly All of the Time	Most of the Time	About Half the Time	Less than Half the Time
Aspirin					
ACE Inhibitor (e.g. Ramipril, Lisinopril,)					
Beta Blocker (e.g. Acebutalol)					
Medication 4 Statin (e.g. Simvastatin)					
ARIIA (e.g. Candesartan)					

Section 4: Clinical Outcomes

1. **Have you experienced any of the following since discharge?** (Check all that apply)
 - Recurrent chest pain
 - Rehospitalization for cardiac issues
 - Stroke
 - Heart failure symptoms
 - No major events
2. **Follow-up with healthcare provider since discharge:**
 - Yes
 - No
 - If Yes, how many visits: _____

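### The objectives and expected outcomes claim adherence for all discharged ACS patients or for Nepal, but only patients who attend or are readmitted at one centre can be sampled, and the plan does not say so

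*Combined protocol and SAP*

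**What the plan says.** The population is described in several ways.

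- Section 5a, general objective: to assess adherence and "identify the factors influencing adherence among patients with Acute Coronary Syndrome (ACS) in Nepal". The research question in Section 6 also refers to ACS patients in Nepal.
- Section 5b, first specific objective: adherence "among patients discharged after an Acute Coronary Syndrome (ACS) event".
- Sections 7.1 and 13: re-hospitalised patients only. Section 13 places them in Nepal.
- Section 7.3, the frame: adults "who have either come to OPD for follow-up or have been readmitted for having cardiac complications months after surviving ACS" at one centre, with "The total population under study is around 1000". It does not say whether that count means discharged patients or returning patients.
- Section 7.5: "we will approach patients who are readily available within the hospital setting". Section 7.10 places recruitment in the cardiology OPD and ward.
- Section 7.4: the centre's mix of urban and rural patients "provides a comprehensive understanding of medication adherence patterns across various demographic and socioeconomic groups".

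Section 9 lists OPD versus re-hospitalised differences, survivor bias and self-report. Section 10 adds heterogeneity, the single centre, the cross-sectional design, incomplete records and confounding. Neither mentions this centre's own discharged patients who do not come back.

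**The concern.** The target and the frame differ. No discharge register, tracing or telephone contact is described, and the online platform in 7.1 is a mode of administration, not a way to reach people who do not attend. Discharged patients who neither attend nor are readmitted here have an inclusion probability of zero, and a larger sample from the same clinics does not change that.

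The omission may be related to the outcome: the Introduction lists accessibility of medical care among the predictors of non-adherence. Sections 13 to 15 intend the results to guide policy and practice recommendations, so a rate for patients in contact with one tertiary centre could be read as a rate for all discharged patients, or for the country.

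**Working it through.** **1. Who can enter.** Divide discharged patients into three groups and compare them with 7.3, 7.5 and 7.10.

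| Group | In objective 1? | Can be sampled? |
|---|---|---|
| Attends this OPD | yes | yes |
| Readmitted here, whether or not they had stopped OPD follow-up | yes | yes |
| Neither attends nor is readmitted here | yes | no |

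The third row is the mismatch. It needs no arithmetic.

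**2. The plan's own figures.** Section 7.6 gives p = 92.5% and a 5-point margin. The check is 1.96² × 0.925 × 0.075 / 0.05² = 106.60 (the plan prints 106.39 and uses 106), and 106 × 1.10 = 116.6, so 117. The declared inputs reproduce the sample size. The printed substitution, with 0.924 and 1 − 0.817, would give 259.8; that is a separate slip and does not bear on this point.

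**3. Direction, as an illustration.** The documents give no loss to follow-up, no readmission share and no planned OPD/ward mix. Apart from 92.5%, every input below is an assumption.

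- OPD attenders adhere at p_o = 92.5%; readmitted patients at p_r = 50–70%; non-returners at p_n = 50–70%.
- Among all discharged patients, r = 10% are readmitted and L = 10–30% are lost.
- s is the share of the sample that is readmitted.

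Observed rate = (1 − s)p_o + s·p_r. Target rate = (1 − L − r)p_o + r·p_r + L·p_n. Subtracting:

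error = L(p_o − p_n) − (s − r)(p_o − p_r)

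| s | Lowest error | Highest error |
|---|---|---|
| 10% | 0.10 × 22.5 = +2.25 | 0.30 × 42.5 = +12.75 |
| 30% | 2.25 − 0.20 × 42.5 = −6.25 | 12.75 − 0.20 × 22.5 = +8.25 |
| 50% | 2.25 − 0.40 × 42.5 = −14.75 | 12.75 − 0.40 × 22.5 = +3.75 |

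The first term is the missing non-returners and pushes the rate up. The second is over-sampling of readmitted patients and pushes it down. The sign depends on s, which the plan leaves open.

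**4. Sensitivity to the anchor.** The 92.5% is the share highly adherent on a four-item Morisky-Green-Levine scale. Section 7.10 here counts as non-adherent anyone who answers less than all of the time for any drug, and the Introduction cites adherence below 50% by 12 months. If attenders adhere at 50% and non-returners at 40%, a loss of 10–40% moves the rate by 0.10 × 10 = 1 to 0.40 × 10 = 4 points, inside the 5-point margin. If non-returners adhere as well as attenders, the non-returner term is zero.

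**The case against.** Part of this is disclosed. The title limits the study to patients attending a tertiary centre, the project summary says readmitted or attending follow-up, and Section 10 concedes that a single centre limits generalisability and that access to healthcare is hard to account for. That stands, and it makes the repair mainly one of wording. It does not remove the point. The objectives and Section 13 drop the title's restriction, the single-centre item concerns other facilities, and access appears only as a confounder, not as something that decides who is sampled.

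Stronger readings are tempting, and the documents do not support them.

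- A reader might infer that anyone who dropped out of follow-up is excluded. A patient who stopped attending but is readmitted here is eligible, and the proforma item "Follow-up with healthcare provider since discharge" has a No option.
- A reader might infer that the rate is overstated, or is an upper bound. That follows only for the non-returner component. Section 4 links poor adherence to recurrent events, so a sample rich in readmitted patients may err low.
- A reader might infer that the rural/urban contrast is understated. That depends on how selection varies jointly with residence and adherence. If distant patients appear mainly when readmitted, the contrast could instead be exaggerated.
- A reader might hope to correct the rate by weighting on visit counts. The proforma counts visits to any provider, records the date of ACS diagnosis but not of discharge, and has no recruitment-setting field. No weight recovers people whose chance of inclusion is zero.

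**Conclusion.** The mismatch between target and frame is established from the text, and Sections 9 and 10 do not disclose it. Followed as written, the plan would report an adherence level for discharged patients, or for Nepal, that the design cannot estimate. What it can estimate is adherence among patients in contact with this centre, in an unstated mix of OPD and ward.

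Neither the sign nor the size of the resulting error can be fixed from the documents. The tabulated range of roughly −15 to +13 points rests on assumed losses, readmission shares and adherence levels, and on an anchor from a different scale. It shows only that the error could exceed the stated 5-point margin in either direction. The correction should be made because it changes what the study can conclude and costs very little.

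**What to change.** - Restate the general and specific objectives, the research question, 7.1 and Section 13 for one population: patients within 12 months of ACS who attend follow-up or are readmitted at this centre.
- Remove from 7.4 the clause that promises a comprehensive picture across demographic and socioeconomic groups.
- Add to Section 9 that discharged patients who neither attend nor are readmitted here cannot be included. Assert no net direction and no rural/urban direction.
- Add an OPD/ward tick box to the proforma, and state in Section 8 that adherence will be reported separately for the two groups.

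The cost is wording, one field on the form and one extra table. The downside is a narrower claim and less precise separate rates. At p = 0.925, the 95% half-width for 106 patients is 1.96 × √(0.925 × 0.075 / 106) = 5.0 points. With an even split, assumed for illustration, each group of 53 has 1.96 × √(0.925 × 0.075 / 53) = 7.1 points.

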7.7 Inclusion and Exclusion criteria

- **Inclusion Criteria:**

1. Patients diagnosed with ACS, including ST-Elevation Myocardial Infarction (STEMI), Non-ST-Elevation Myocardial Infarction (NSTEMI), or Unstable Angina within the last 12 months.
2. Patients aged 18 years and older.
3. Patients willing to participate and provide informed consent for the study.

- **Exclusion Criteria:**

1. Individuals who have not been diagnosed with ACS or those with other acute or chronic conditions that might influence medication adherence unrelated to ACS.
2. Patients with cognitive impairments or mental health issues that prevent them from understanding or responding accurately to the study questionnaires.
3. Patients with severe chronic conditions (e.g., terminal illness, advanced dementia) that may affect their ability to adhere to medication regimens.

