7.8 Study variables

Dependent Variable:

- **Adherence to Secondary Prevention Medications (SPMs):** This includes adherence levels to specific medications such as antiplatelets, statins, beta-blockers, and ACE inhibitors/ARBs, measured through MYMEDS questionnaire.

Independent Variables:

1. Demographic Factors:

- Age
- Gender
- Education Level
- Occupation
- Place of Residence (Rural vs. Urban)
- Monthly Income

2. Clinical Characteristics:

- Type of Acute Coronary Syndrome (e.g., STEMI, NSTEMI, Unstable Angina)
- Comorbidities (e.g., Hypertension, Diabetes Mellitus, Dyslipidemia, Chronic Kidney Disease)

3. Patient-Reported Factors:

- Concerns about medication side effects
- Pill burden (number of medications)
- Practical issues with medication administration (e.g., difficulties opening bottles)
- Difficulty integrating medications into daily routines

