 - 4. Semi-skilled worker**
 - Factory or workshop laborer, laboratory or library attendant, car cleaner

5. Unskilled worker

- Watchman, peon, domestic servant, rickshaw puller

6. Unemployed

9. **Family Monthly Income (NPR):** _____

- $\geq 97,451$
- 48,751–97,450
- 36,551–48,750
- 24,351–36,550
- 14,551–24,350
- 4,851–14,550
- $\leq 4,850$

10. **Place of Residence:**

- [] Rural
- [] Urban

11. **Distance from Healthcare Facility:** _____ (km)

Section 2: Clinical Information

1. **Type of ACS:**

- [] ST-Elevation Myocardial Infarction (STEMI)
- [] Non-ST-Elevation Myocardial Infarction (NSTEMI)
- [] Unstable Angina

2. **Date of ACS Diagnosis:** _____

3. **Treatment Received:**

- [] Percutaneous Coronary Intervention (PCI)
- [] Coronary Artery Bypass Grafting (CABG)
- [] Medical Management Only

4. **Comorbidities:**

- [] Hypertension
- [] Diabetes Mellitus
- [] Dyslipidemia
- [] Chronic Kidney Disease
- [] Stroke
- [] Peripheral Arterial Disease
- [] Others (Specify): _____

Section 3: Assessment of Adherence**MYMEDS Questionnaire****Section 1: Current Medicines**

Serial Number	Name of Medicines	Administration Time (Morning/Afternoon/Evening/Night)	Reason for Taking Medicine
1	Antiplatelets	_____	_____
2	Statins	_____	_____
3	Beta-blockers	_____	_____
4	ACE inhibitors/ARBs	_____	_____
5	Others (Loop diuretics, Nitrates, specify)	_____	_____

Section Number	Statement	Strongly agree	Agree	Disagree	Strongly disagree
Section 2: Understanding and satisfaction with medicines	a. I fully understand my heart medicines and why they were prescribed.				
	b. My heart medicines seem to be working for me.				
	c. I feel convinced of the importance of all my heart medicines.				
	d. At least occasionally, I need to alter my medicines on my own to make them work or meet my expectations.				

Section 3: Concerns about medicines	a. I worry that one or more of my medicines will do me more harm than good.				
	b. I feel concerned about being prescribed too many medicines.				
	c. I sometimes alter my medicines by cutting back or stopping taking them. (e.g. due to feeling worse, getting worried or for any other reason)				
Section 4: Practical issues that may be a barrier to adherence	a. I have difficulties or problems opening the medicine bottles or blister packs and would like a solution or an alternative.				
	b. I have difficulties or problems swallowing my medicine(s) and would like a solution or an alternative.				

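### Objective 4 relates past-month adherence to undated events since discharge, and the visible form records neither recruitment setting nor event dates, so it cannot separate earlier events from current readmissions or show the OPD/ward mix.

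*Combined protocol and SAP*

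**What the plan says.** Section 5 lists, as the last specific objective, "To evaluate the relationship between medication adherence and clinical outcomes", with recurrent cardiac events and rehospitalization as the examples. The project summary repeats the aim: "analyzing these with SPSS to assess correlations with clinical outcomes".

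The data come from the proforma in the annexes:

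- **Adherence.** MYMEDS Section 6 reads "please indicate how often you have taken them as prescribed in the PAST MONTH". Section 7.10 describes the same one-month window.
- **Outcomes.** Proforma Section 4 asks "Have you experienced any of the following since discharge" and offers boxes for recurrent chest pain, cardiac rehospitalization, stroke, heart failure symptoms or no major event. More than one may be ticked, and none carries a date.
- **Dates.** The only date field is "Date of ACS Diagnosis". Follow-up visits are counted but not dated.

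Section 7.7 admits patients with STEMI, NSTEMI "or Unstable Angina within the last 12 months". Sections 7.3 and 7.5 recruit from OPD follow-up and from readmissions, whereas sections 7.1 and 13 describe re-hospitalized patients only. The variable list in 7.8 contains no recruitment setting, no timing variable and no clinical outcome.

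Section 7.4 cites "access to detailed patient records" as a strength of the site, and section 7.9 includes medical record review in data collection. Neither says which items will be extracted. Section 8 shows topic prompts without an analysis method.

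**The concern.** A reader of objective 4 will want to know whether patients who took their medicines less reliably had more events. That requires knowing whether the adherence measured came before or after the event. Here the adherence window is one month and the event window can approach twelve, so many ticked events may lie wholly before the month being reported. A readmission may itself change how a patient takes medicines, in either direction.

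Recruitment setting matters as well. Ward patients enter the study because they were readmitted, and readmission is one of the outcomes in objective 4. Section 9 warns that OPD and re-hospitalized patients may differ in adherence and that this could bias their comparison, yet the form has no field for which group a patient belongs to. Convenience sampling leaves the mix uncontrolled, so a reader of the pooled rate could not tell what mixture it describes.

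**Working it through.** **1. The windows.** Adherence covers 1 month (7.10, MYMEDS Section 6). Events run from discharge to interview, with ACS up to 12 months earlier (7.7). For a patient interviewed at 12 months, up to 12 − 1 = 11 months of the event window precede the adherence month. The figure is slightly less in practice, because discharge follows diagnosis.

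**2. What the form can distinguish.** Take three hypothetical patients who all tick rehospitalization:

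- seen in OPD, readmitted eight months ago: the reported month lies wholly after the event;
- on the ward, just readmitted: the reported month lies almost wholly before it;
- readmitted two weeks before interview: about half before and half after.

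No visible field need differ between them. The tick does not mark setting either, since an OPD patient may have been readmitted earlier. If every ward patient ticks it for the current stay, the share ticking is an upper bound on the ward share and no more.

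**3. Direction.** Let f be the share of patients with an event whose reported month is wholly post-event. Treating the rest as pre-event for simplicity,

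observed adherence with an event = (1 − f) × pre-event adherence + f × post-event adherence.

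Suppose pre-event adherence is below that of event-free patients. The association is then unchanged if post-event adherence equals pre-event, weakened if it is higher and strengthened if it is lower. It reverses only if the weighted average exceeds the event-free level. The documents give none of these quantities, and the form does not record f.

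**4. Mix.** Change in pooled rate = change in OPD share × (OPD adherence − ward adherence). As an assumption only: over a change in OPD share from 20% to 80%, a gap of 5/0.60 = 8.3 points moves the pooled rate by 5 points, the planned margin of error. From an even mix to either end, the gap needed is 5/0.30 = 16.7 points.

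**5. Precision.** The plan's own figure comes first. With z = 1.96, p = 0.925, d = 0.05 (7.6), n = 1.96² × 0.925 × 0.075 / 0.05² = 106.6, which agrees with the stated 106. Adding 10% gives 106 × 1.10 = 116.6, or 117. The substitution printed in 7.6 contains other values, which is a separate matter.

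- Expected non-adherent: 106 × 0.075 = 7.95, about 8, leaving 98 adherent.
- The standard error of a log odds ratio is smallest when both groups divide evenly between event and no event: √(1/4 + 1/4 + 1/49 + 1/49) = 0.735. Since exp(1.96 × 0.735) = 4.2, a 95% interval runs at best from the estimate divided by 4.2 to the estimate multiplied by 4.2.
- Half-width for adherence, 1.96 × √(0.925 × 0.075 / n): 5.0 points at n = 106 and 7.1 points at n = 53. With 53 × 0.075 ≈ 4 non-adherent per setting, the normal approximation is rough.

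**The case against.** The strongest reply is that the plan may already obtain these data. The form carries a patient ID, the site has detailed records, record review is planned, and 7.10 says a questionnaire is still to be developed. The flow diagram under 7.13, whose heading mentions assessment timing, is not in the text available for review, and an interview date could sit on a page that is also not there. This stands as a limit on the claim. A reader might infer that timing and setting will be lost for good, and the documents do not support that. What they show is that no visible field, listed variable or named extraction item secures them.

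Second, the study calls itself descriptive and cross-sectional, objective 4 speaks of a relationship and not an effect, and sections 9 and 10 disclose OPD/ward differences and the single time point. That is fair, and it lowers the stakes. But neither section mentions the unequal windows, and a caveat cannot supply a date that was never written down.

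Third, imprecision may swamp the problem. With about 8 non-adherent patients, a table by event timing will have nearly empty cells. This also stands. It argues for description over testing, not for leaving event order unrecorded.

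A reader might go further and infer that the association will be pulled towards the null or reversed. Step 3 of the working shows that this depends on post-event adherence, which the documents do not give. Nor is an index discharge date needed: ordering depends on event date against interview date.

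**Conclusion.** The point holds for the form as annexed, and it should be fixed. Objective 4 cannot be interpreted in time order from that form, and the OPD/ward mix behind the pooled rate can be bounded at most, not identified. The finding rests on reading the fields and needs no numerical assumption. It is certain for the visible proforma and less so for the plan as a whole, given the unspecified record review and the absent diagram.

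The size of any distortion cannot be stated. The precision figures rest on the plan's 92.5% adherence being borne out and on 106 responders. Objective 1 is not invalidated: a pooled rate for the patients recruited can still be estimated, though its mixture would be unknown.

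**What to change.** 1. Add to the proforma recruitment setting (OPD or ward), interview date, and the date of each readmission or recurrent event. A first-event date alone would misplace a ward patient who also had an earlier event. For chest pain and heart failure symptoms, record onset or note that they are ongoing. Complete these at interview or from the planned record review, and name the items that review will extract.
2. Report adherence by setting alongside the pooled rate.
3. Report objective 4 descriptively. Tabulate patients whose only events preceded the recall month separately from those with an event within it or a current readmission. Note that for an event within the month the measured adherence is only partly pre-event.
4. State the window mismatch as a limitation, and reconcile the population in 7.1 and 13 with that in 7.3 and 7.5.

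The cost is a few short fields, two descriptive tables and some wording. If interviews have begun, the patient ID and records may allow the fields to be filled retrospectively. Setting-specific intervals will be wider and timing cells sparse. Dates show the order of events and adherence, but they do not recover pre-event adherence for patients interviewed long after an event.
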